### **3.4 Protocol deviations**

Important protocol deviations (IPD) are those deviations from the protocol identified by the study team as important which will be summarized in the clinical report, in accordance with ICH E3. The criteria for identifying important protocol deviations will be defined within the appropriate protocol-specific document at study start. All protocol deviations will be reviewed periodically through the study as part of the ongoing data cleaning process and those identified as important will be documented prior to final database lock and integrated into the clinical database.

### **3.5 Analysis sets**

Primary and other safety endpoints will be analyzed using the Safety Set (SS). Primary and other efficacy endpoints will be analyzed using the Full Analysis Set (FAS).

These analysis sets are described below.

#### **3.5.1 Enrolled Set**

The Enrolled Set (ES) will consist of all subjects who have signed the ICF.

### 3.5.2 Safety Set

The Safety Set (SS) will consist of all enrolled subjects who were administered at least 1 dose of PSL, based on the first dose date from the First Administration of Study Medication CRF.

### 3.5.3 Full Analysis Set

The Full Analysis Set (FAS) will consist of all enrolled subjects who were administered at least 1 dose of PSL or a partial dose of PSL and completed at least 1 seizure diary during the Evaluation Period.

## 3.6 Treatment assignment and treatment groups

The individual starting dose of each subject will be the one recommended at the end of the parent study. Further individual dose adjustments are allowed between 100mg/day up to a maximum of 800mg/day to the extent possible with combination of tablet strengths available (ie, 25mg, 100mg, and 200mg).

## 3.7 Sites pooling strategy

Pooling strategy is not planned for this study.

## 3.8 Coding dictionaries

All prior and concomitant medications other than study drug will be classified by World Health Organization WHO Anatomical Therapeutic Chemical (ATC) Classification, presenting Anatomical Main Group (ATC Level 1), Pharmacological Subgroup (ATC level 3), and preferred term, using Version SEP/2017 or higher of the World Health Organization Drug Dictionary (WHO-DD). Coding will be performed in accordance with UCB standard operating procedures (SOP).

Medical history and AEs will be coded by primary system organ class (SOC), high level term (HLT) and preferred term (PT) using version 22.1 or higher of Medical Dictionary for Regulatory Activities (MedDRA®) according to UCB Standard Operating Procedures (SOP).

## 3.9 Changes to protocol-defined analyses

Due to the COVID-19 impact on site initiation and enrollment as well as early termination of the study, the following items in the protocol were updated in the SAP

Section in this SAP	Description	Change from the protocol
Table 2-1:	Schedule of Assessments	Added: Setting (Required Onsite) column to include data that may be collected through phone or video calls for visit, during the pandemic.

3.10	COVID-19 eCRF	Added, see section 3.10 for details
4.4	Examination of subgroups	Removed China as a region
10.2.1.8	Derivation of other efficacy variables	
Removed: Drug Loads of AEDs
 
Changes in drug load are captured by number of products and daily dose per given product recorded in the AED Medication CRF. Drug load will be assessed using ratio of actual daily dose and World Health Organization defined daily dose (DDD).  “https://www.whocc.no/atc_ddd_index/?code=N03A&showdescription=no”.
 
The daily dose of the administered AED will be calculated at Entry Visit, Visit 8, and EOS. All AEDs which has the stop date at the visit (EV, Visit 8, EOS) or ongoing and the start date prior to the visit will be considered administered at that specific visit.
 
The drug load of all AEDs will be calculated as the sum of ratios of dose and DDD for each of the AEDs at the respective visit. The drug load of each AED class will be calculated as the sum of ratios of dose and DDD for each of the AEDs within the AED class. AED classes included in this analysis are:
 
 
• SV2A: levetiracetam and brivaracetam
 
• BZD: ATC code N05BA
 
• sodium channel-blocking AED (SCB (+): carbamazepine, oxcarbazepine, eslicarbazepine, phenytoin and lamotrigine
 
 
Ratio of dose and DDD, absolute change from EV in the ratio, and percent change from EV in the ratio will be summarized by all AEDs, AED drug class and by each of the AEDs. For two visits, the absolute change of a given AED drug load can be calculated if the product is administered at one of the visits; and the percent change can only be calculated if the AED is administered at EV. The change in number of all AEDs at Visit 8 and EOS relative to EV will also be summarized.

11	COVID-19	The impact of COVID-19 global pandemic on this study is detailed in section 3.10. COVID-19 impact will be listed by

	Impact	impacted visit, date, impact category, and relationship to COVID-19 (confirmed, suspected, general circumstances around COVID-19 without infection or other) for each subject in the ES.
15	Addendum	Added:  All tables described in the SAP will be repeated for Japan and non-Japan subgroups.

### 3.10 COVID-19 eCRF

A new COVID-19 eCRF, to evaluate the impact of global pandemic was created and implemented to collect the information on impacted visit, impact category, and relationship to COVID-19.

Listing and table (see Section 11 for details) to describe the impact on the interpretability of efficacy and safety endpoints will be performed to assess the impact of the changes on the planned analyses due to COVID-19.

## 4 STATISTICAL / ANALYTICAL ISSUES

General statistical and analytical issues are provided in the following sections.

### 4.1 Handling of dropouts or missing data

#### 4.1.1 Handling of missing data in seizure frequency

Seizure frequency will be calculated over non missing diary days during an analysis period or time interval. Days with missing seizure diary (ie, "Not Done" is ticked on the Seizure Count CRF) will not be considered in the calculation of seizure frequency or seizure free days. No imputation will be applied to missing seizure diary data. Seizure frequency during a time interval will be calculated if seizure data are available for at least 1 day during the interval.

#### 4.1.2 Handling of missing data for adverse events and concomitant medications

For analyses of AEs and concomitant medication usage, a complete date must be established to correctly identify the AE or medication as occurring during treatment or not. In the event of completely missing dates, or if ambiguity or incomplete data makes it impossible to determine whether a medication was concomitant, or an adverse event was treatment emergent, the medication will be considered as concomitant or the adverse event will be considered treatment emergent.

For purposes of imputing missing components of partially-reported start and stop dates for AEs and for medication use, the algorithms listed below will be followed. Start and stop dates of AEs or concomitant medication will be displayed as reported in the subject data listings (i.e., no imputed values will be displayed in data listings). Note that imputed times and dates should not be presented in the patient data listing.

Partial AE and concomitant medication start dates will be imputed as described in the following sections.

#### **4.1.2.1 Imputation of Partial Start Dates**

- If only the month and year are specified and the month and year of first dose is not the same as the month and year of the start date, then use the 1st of the month
- If only the month and year are specified and the month and year of first dose is the same as the month and year of the start date, then use the date of first dose
- If only the year is specified, and the year of first dose is not the same as the year of the start date, then use the 1st of January of the year of the start date
- If only the year is specified, and the year of first dose is the same as the year of the start date, then use the date of first dose
- If the start date is completely unknown and the stop date is unknown or not prior to the date of first dose, then use the date of first dose.
- If the imputed start date is after the known stop date, set the start date to be the same as the stop date.

#### **4.1.2.2 Imputation of Partial Stop Dates**

- If only the month and year are specified, then use the last day of the month
- If only the year is specified, then use December 31st of that year
- If the stop date is completely unknown, do not impute the stop date

#### **4.1.3 Incomplete dates for first epileptic seizure**

To calculate the time since the first seizure relative to the date of EV of EP0093 at onset of first seizure, a complete date will be imputed for partially missing first seizure date as following:

- Missing the day, but month and year present  
Assign the 1st day of the month.
- Missing the day and month, but year present  
Assign January 1st of the year.
- Completely missing  
No imputation will be done.

## 4.2 Interim analyses and data monitoring

No formal interim analysis is planned. However, data may be reported prior to the completion of this study to support annual reports, regulatory submissions, and publications.

A Data Monitoring Committee (DMC) will be formed to monitor the ongoing safety of the study through periodic review of data summaries. The general scope of DMC activities is presented in the protocol and will be described in detail in a separate DMC Charter. Preparation of data summaries for review by the DMC will be described in a separate DMC SAP.

## 4.3 Multicenter studies

In generally, efficacy and safety summaries and analyses will be presented across investigative sites, countries and regions.

## 4.4 Examination of subgroups

Selected summaries will be provided for the following subgroups:

- Region

Countries will be stratified to geographic regions as follows:

Geographic region	country
North America	Canada, US, Mexico
Europe	Australia, Austria, Belgium, Bosnia and Herzegovina, Bulgaria, Croatia, Czech Republic, Denmark, Estonia, Finland, France, Germany, Greece, Hungary, Ireland, Italy, Lithuania, Netherlands, Norway, Poland, Portugal, Romania, Serbia, Slovakia, Spain, Sweden, Switzerland, Turkey, United Kingdom.
Japan	Japan

Further sites in countries not yet included in this table are possible.

# 5 STUDY POPULATION CHARACTERISTICS

## 5.1 Subject disposition

Screen failure data of screened subjects who did not meet study eligibility criteria are collected on the Study Termination CRF (dates of screen failure and last contact and reason for screen failure).

Details on the last study visit are obtained from the Study Termination CRF. Variables include date of last administration of study medication, date of final contact with the subject, subject

status at study termination, date of premature study termination and primary reason for premature study termination (as listed on CRF).

The disposition of subjects will be summarized for the ES, and SS overall and by region, country as well as by investigator.

Summaries of the numbers of screened subjects and reasons for screen failures will be produced overall for the ES.

The disposition will also be presented as the number and percentage of subjects who started, completed or discontinued the study. Discontinuation of study includes a breakdown of primary reasons for discontinuation. These tables are presented overall and by region for the SS.

The number and percentage of subjects in the SS who discontinued due to AE categorized by serious fatal, non-fatal, and non-serious fatal AE incidence will also be summarized for the SS. Of note, the corresponding table is required for data transparency reporting.

Listings will be provided for disposition, reason for discontinuation and visit dates.

## 5.2 Protocol deviations

IPDs are defined in [Section 3.4](#). All IPDs will be listed by subject and will include, at a minimum, deviation type (as collected under the important deviation collection plan), deviation number, deviation description, and date of deviation.

Important protocol deviations will be reviewed as part of the ongoing data cleaning process prior to database lock. After all data have been verified/entered into a database and prior to database lock, a final data evaluation meeting will take place. Protocol deviations will not lead to exclusion from any analysis set.

A summary of number and percentage of subjects with an IPD will be produced for the SS. The summary will be overall (any IPD) and by type of deviation.

## 6 DEMOGRAPHICS AND OTHER BASELINE CHARACTERISTICS

### 6.1 Demographics

Demographic variables are collected on the Demographics CRF. The following demographic variables will be summarized for the SS by region:

Based on data collected at EV of EP0093:

- Age (in years)
- The following age categories will be summarized in the same table: (i)  $\leq 18$  years, 19 - <65 years and  $\geq 65$  years; (ii) 18- <65 years, 65 - <85 years and  $\geq 85$  years

Based on data collected at study entry of the parent study:

- Sex (male, female)
- Race (all categories on the CRF)
- Ethnicity (Hispanic or Latino, not Hispanic or Latino)
- Ethnic sub-group (Japanese, non-Japanese)
- Height (in cm)
- Weight (in kg)
- Body mass index (BMI) (kg/m^2) and BMI category (<18.5, 18.5 to <25, 25 to <30, 30 to <40, ≥40)
- Vagus Nerve Stimulation (Yes, No)
- Parent study (EP0091, EP0092)

## **6.2 Other baseline characteristics**

The following data collected at the time of entry into the parent study will be summarized for the SS. The parameters derived in the parent will be directly used.

- Number of lifetime AEDs taken prior to the parent study: <4, 4 or 5, 6 or 7, 8 to 10, >10 AEDs. Lifetime AEDs is defined as AEDs with the start date prior to study entry including prior AEDs on AED medication CRF and previous AEDs on History of Previous Antiepileptic Drug Treatment eCRF.
- Number of AEDs taken at the entry of the parent study: 1, 2, 3, and > 3 AEDs
- Current use of AEDs with binding to SV2A proteins (LEV and/or BRV): Yes or No

## **6.3 Medical history and concomitant diseases**

### **6.3.1 Medical history**

Medical history reported at the entry of the parent study and any medical history update will be summarized and listed for the SS by MedDRA system organ class (SOC) and preferred term (PT). The start date (month and year only) and end date (or ongoing if applicable) will be included in the listing.

A medical history update is done at the Entry Visit. Of note, medical history update CRF should only be used after the database of the parent study is already locked. All efforts will be taken to make sure medical history are completed in the database of the parent study.

### **6.3.2 Medical history of epilepsy**

Selected medical history of epilepsy collected at the entry of the parent study will be summarized for the SS.

### **6.3.2.1 Epileptic seizure profile**

Epileptic seizure profile is based on the historical seizure types reported by the subject on the ILAE Seizure Classification History form. The number and percentage of subjects experiencing each seizure type at any time in the past will be summarized.

### **6.3.2.2 History of epileptic seizures and diagnosis of epilepsy**

History of epileptic seizures, including the number and percentage of subjects with a history of status epilepticus, the number and percentage of subjects with a history of withdrawal seizures, and quantitative summaries of time since first seizure relative to the Entry Visit of EP0093 (ie, Entry Visit of EP0093 minus the date of the first epileptic seizure plus 1 divided by 365.25) and the age at onset of first seizure will be summarized for the SS.

## **6.4 Concomitant medications**

Concomitant AED and non-AED medication are collected on separate CRFs. These include the AED Medication CRF and the Concomitant medication CRF. All concomitant medication started in the parent studies and are ongoing at the time of Entry Visit in EP0093 are collected on separate CRFs (Prior and Concomitant Medications\_Parent Study CRF, AED Medication\_Parent Study CRF).

A medication will be included in a concomitant summary if:

- (Date of first dose of PSL in EP0093)  $\leq$  (Start date of medication)  $\leq$  (Date of last dose of PSL in EP0093); or
- Start date of medication is prior to the first dose of PSL in EP0093 or unknown, but medication is ongoing at study entry.

### **6.4.1 AED medication**

The number and percentage of subjects taking concomitant AED medications will be summarized by chemical/therapeutic/pharmacological subgroup (ATC classification level 4), and preferred drug name.

### **6.4.2 Use of vagus nerve stimulation**

The number and percentage of subjects with Vagus Nerve Stimulation (VNS) in Previous Study (collected at EV) will be summarized. Subjects with VNS setting changed during the Evaluation Period will also be summarized. All other VNS data will be provided in subject data listings and will not be summarized for the SS.

### **6.4.3 Non-AED medication**

The number and percentage of subjects (SS) taking non-AED medications will be summarized by anatomical main group (Anatomical Therapeutic Chemical [ATC] classification level 1), therapeutic subgroup (ATC classification level 2), and preferred drug name.

## 7 MEASUREMENTS OF TREATMENT COMPLIANCE

Information reported on the CRF regarding the number of tablets dispensed and returned and doses taken in the morning and evening will be reported in subject data listings. Drug accountability is recorded on the Drug Accountability form. Measurement of treatment compliance with the dosage schedule will be based on dispensed and returned pill counts. Drug accountability data will be listed (SS) by treatment group and study visit. The listing will include dispense date and number of pills dispensed; return date and number of pills returned.

PSL treatment compliance will be evaluated through the review of important protocol deviations.

## 8 PHARMACOKINETICS AND PHARMACODYNAMICS

No pharmacokinetic or pharmacodynamic analyses will be conducted.

## 9 SAFETY ANALYSES

All safety analysis will be provided for the SS.

### 9.1 Extent of exposure

The overall duration of exposure of the study will be calculated as the date of last dose of PSL minus the date of first dose of PSL (Section 3.2.2.1) in EP0093 plus 1 day.

Modal daily dose of a subject will be calculated as the daily dose the subject received for the longest duration during EP0093. In the event of a tie, the modal dose will be set to the lower of the tied doses. Modal daily dose will be categorized as  $\leq 200$ mg/day,  $> 200$ mg/day to  $\leq 400$ mg/day,  $> 400$ mg/day to  $\leq 600$ mg/day, and  $> 600$ mg/day.

The duration of exposure will be summarized overall and by modal dose for the SS and by region:

- Cumulative months of exposure: duration of exposure in days will be summarized. Duration of exposure will also be categorized into the following cumulative months categories of exposure:  $\geq 3$  months,  $\geq 6$  months,  $\geq 9$  months,  $\geq 12$  months,  $\geq 18$  months, and  $\geq 24$  months.

Listings will include the study medication exposure per subject and the administration of study medication per dispense interval. Data collected on the Prescribed Padsevonil Dose CRF will be listed.

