7.2 Treatments to be administered

Padsevonil will be administered in an open-label manner. All subjects will be instructed to take 2 doses approximately 12 hours apart each day 30 minutes after food when practically feasible. The individual starting dose of each subject will be the one at the end of the parent study. The

first dose of the study will be the dose on the day of Visit 1. Once subjects enter EP0093 further individual dose adjustments are allowed after 1 week, between 100mg/day up to a maximum of 800mg/day to the extent possible with the combination of tablet strengths available (ie, 25mg, 100mg and 200mg). Integrity of the tablets should not be tampered with (eg, cut) to obtain lower dosages. Twice daily dosing with equivalent morning and evening doses approximately 12 hours apart is deemed necessary to ensure more regular exposure over the 24-hour interval; however, the dosing schedule may be adjusted as needed to improve tolerability and efficacy. The decision to advise subjects to divide their morning and evening daily dose unequally should be documented in the eCRF and the UCB Study Physician or delegate should be notified. Increases or decreases to the dose of PSL should not exceed a maximum 200mg/day per week. A faster/slower decrease/increase of the dose than 200mg/day per week is allowed in case of emergency in the Investigator's medical judgment.

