9.3.8 Withdrawal monitoring

Any symptoms of withdrawal reactions will be monitored using the CIWA-B questionnaire at the scheduled time points presented in [Table 5-1](#). The CIWA-B questionnaire contains questions and observations which are selected to distinguish withdrawal symptoms from other symptoms (Busto et al, 1989).

Subjects should be monitored during the Taper Period for withdrawal symptoms, including withdrawal-related AEs or seizures as well as the severity of the CIWA-B withdrawal scores. Withdrawal symptoms may require medical treatment for management of severe withdrawal symptoms.

Further details about this questionnaire will be covered in the Study Manual.

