**Table 2-1: Schedule of assessments**

	Setting (Required Onsite s )	Evaluation Period a								Taper Period (including 1 Wk drug free)	SFU (30 days after last PSL intake)	Unsch Visit/TC	
		Entry Visit	Bi-weekly Visits		Monthly Visits		Visits every 3 M		EOS Visit				EDV Visit
		V1 b	V2	V3	V4	V5	V6, V8, V10	V7, V9, V11	EOS c				EDV c
Assessments		Wk 0	Wk 2	Wk 4	M2	M3	M6, M12, M18	M9, M15, M21	M24		Up to 4 Wk		
Study termination	NA – this is not an assessment								X q		X r		

AED=antiepileptic drug; BP=blood pressure; CIWA-B=Clinical Institute Withdrawal Assessment-Benzodiazepines; C-SSRS=Columbia-Suicide Severity Rating Scale; ECG=electrocardiogram; EDV=Early Discontinuation Visit; EOS=End of Study; HADS=Hospital Anxiety and Depression Scale; HRU=healthcare resource utilization; IRT=interactive response technology; M=month; PSL=padsevonil; QOLIE-31-P=Quality of Life Inventory in Epilepsy-31-P; SFU=Safety Follow-up; SSG=Seizure Severity Global Item; TC=telephone call; TSQM=Treatment Satisfaction Questionnaire for Medication; Unsch=unscheduled; V=visit; Wk=week, NA=Not Applicable

a At any point during the Evaluation Period, an unscheduled visit may be conducted due to safety or efficacy reasons. Appropriate assessments will be conducted in relation to the reason for the visit. If an unscheduled visit is conducted due to safety or efficacy reasons, a C-SSRS assessment will be performed with the subject during the visit. If an unscheduled visit is conducted for reasons other than safety or efficacy concerns (eg, replacement of lost medication, repeated collection of a laboratory specimen due to collection or analysis issues), a C-SSRS will not be required at these visits.

b Entry Visit (Visit 1) will be done on the same day as the last visit of parent study. Data from parent study will be used (identified by \*) and corresponding assessments will not be repeated.

c The Taper Period is only valid for subjects discontinuing the study or completing without continuation of the PSL treatment. This period will last for 3 weeks plus a 1-week drug-free period.

d Questionnaires to be completed by all subjects prior to any other study procedures at the visit, when possible.

e Assessment is only valid for subjects discontinuing PSL treatment.

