**Table 3–3.21: Start and end of EP0093 analysis periods**

Description	Start	End	Details
Evaluation Period	Entry Visit (EV, Visit 1)	EOS or EDV or the last contact date if neither EOS or EDV visit is available.  At the time of a clinical cutoff prior to the study completion, if a subject is ongoing and doesn't have the EDV, the end of the period is set to the clinical cutoff date.	The Entry Visit (EV, Visit 1) will be done on the same day as the last visit of the parent study. Subjects will return to clinic every 2 weeks during Month 1, every month during Month 2-3, every 3 months after Month 3 up to Month 24.
Taper Period/ Safety Follow-Up Period	1 day after end date of evaluation period.	The date of final contact.  At the time of a clinical cutoff prior to the study completion, if a subject is ongoing, the end of the period is set to the clinical cutoff date.	Applies only to patients who discontinue the study or complete it without continuation of PSL treatment.
Exposure Period	Date of first dose of PSL	Date of last dose of PSL	Extends from the date of first dose until the last dose of PSL in EP0093. It may include the Evaluation and Taper Period. (Section 3.2.2.1).

At the time of a clinical cutoff prior to the study completion, subjects without the Study Termination eCRF will be classified as “ongoing.” Only the data on or prior to the clinical cutoff date will be included in the analyses.

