### 9.2 Adverse events

Adverse events are recorded on the Adverse Event CRF as they occur, from the time informed consent is granted until study completion or study termination (end of the SFU period 30 days after the last IMP intake). Also, adverse events ongoing at the Entry Visit in EP0093 will be recorded in the Adverse Event\_Parent Study CRF.

A treatment-emergent adverse event (TEAE) is defined as any event not present prior to the initiation of the first dose of study treatment in this study or any unresolved event already present

before initiation of the first dose that worsens in intensity following exposure to the treatment. TEAEs are AEs with start dates on or after the date of first dose of PSL in EP0093. The number and percentage of subjects who experience TEAEs at any time during the study will be summarized (using the SS) by SOC and PT.

Unless noted otherwise, TEAEs during the study will be summarized. At the time of a clinical cutoff, TEAEs with onset date prior to or on the clinical cutoff date will be included. TEAEs are assigned into an analysis period or time interval based on the start date. Adverse event summaries will be ordered in terms of decreasing frequency for SOC, and PT within SOC. The following tabular summaries will be presented for the SS:

- Ongoing AEs at EP0093 study entry
- Incidence of TEAEs during the Study – Overview by Region
- Incidence of TEAEs by Region
- Incidence of TEAEs by 3-month time interval during the Exposure Period
- Incidence of Serious TEAEs
- Incidence of TEAEs by Relationship
- Incidence of SAEs by Relationship. Of note, this table is needed for data transparency reporting.
- Incidence of Fatal TEAEs by Relationship. Of note, this table is needed for data transparency reporting.
- Incidence of TEAEs by Maximum Intensity
- Incidence of TEAEs leading to discontinuation (ie, drop out)
- Incidence of TEAEs leading to dose reduction
- Incidence of TEAEs occurring in at least 5% of Subjects
- Incidence of TEAEs by Dose at Onset ( $\leq 200\text{mg/day}$ ,  $>200\text{mg/day}$  to  $\leq 400\text{mg/day}$ ,  $>400\text{mg/day}$  to  $\leq 600\text{mg/day}$ , and  $>600\text{mg/day}$ ) during the Exposure Period.
- Incidence of Non-Serious TEAEs above the Threshold of 5% of Subjects. This table is needed for data transparency reporting.

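### The only TEAE table by dose counts events arising during taper in lower dose bands and no listed summary separates them; modal dose also counts taper days, with a narrower effect

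*SAP*

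**What the plan says.** **Events by dose.** SAP 9.2 lists a table, "Incidence of TEAEs by Dose at Onset", for the Exposure Period. It has four bands: ≤200, >200 to ≤400, >400 to ≤600 and >600 mg/day. No other TEAE table in that list is split by dose. The table of analysis periods in SAP 3.2.3 says of the Exposure Period: "Extends from the date of first dose until the last dose of PSL in EP0093", and then "It may include the Evaluation and Taper Period". Nothing in the SAP assigns an event that starts in taper to the dose taken before taper.

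**Modal dose.** SAP 9.1 says "Modal daily dose of a subject will be calculated as the daily dose the subject received for the longest duration during EP0093", and "In the event of a tie, the modal dose will be set to the lower of the tied doses". The same four bands apply. Taper dosing is not excluded. Modal dose is used only to summarise duration of exposure.

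**Taper.** Protocol 7.2 sets a rate limit: "Increases or decreases to the dose of PSL should not exceed a maximum 200mg/day per week", with an exception for emergencies. Neither document gives a step schedule. A footnote to the schedule of assessments says "This period will last for 3 weeks plus a 1-week drug-free period". The study description (Protocol 5.1, SAP 2.3) instead speaks of four weeks of tapering, with a visit one week after the last intake. Protocol 9.3.8 expects events in this phase: "Subjects should be monitored during the Taper Period for withdrawal symptoms, including withdrawal-related AEs or seizures".

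**Events by period.** Protocol 12.3 plans TEAE summaries separately for the Evaluation, Taper and SFU periods. The SAP 9.2 list contains no such table, and SAP 3.9, which sets out the changes from the protocol's analyses, does not mention dropping it.

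**The concern.** The primary objective is safety and tolerability at individualized doses from 100 to 800 mg/day, and TEAE incidence is a primary safety variable. Protocol 2.5 describes AEs as tending to be dose-related, so a reader will look to the dose-at-onset table for that relation.

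The table mixes two kinds of exposure. One is time on a low dose as ongoing treatment; the other is time passing through a low dose on the way off a higher one. Withdrawal events belong to the second kind but would sit in the same cells as the first. Adding time-at-dose denominators would not cure this, because the event would still be credited to the wrong kind of exposure.

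The SAP was amended for early termination of the study, which makes short stays followed by taper more plausible than under the planned two years. Subjects who move on to continued PSL may skip the taper and are unaffected.

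**Working it through.** The documents give no figure on this point to reproduce. The check applies the SAP's rules to example dosing histories.

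**Inputs**
- Bands, modal-dose rule and tie rule: SAP 9.1 and 9.2.
- Exposure Period, first to last PSL dose: SAP 3.2.3.
- Maximum rate of 200 mg/day per week, and first dose change after 1 week: Protocol 7.2.
- Assumption: 200 mg/day steps of 7 days each. From 800 mg/day this gives 600, 400 and 200 for 3 × 7 = 21 days, which matches the schedule footnote's three weeks of taper dosing. Variants checked: 10-day steps, and 100 mg/day steps from 400 mg/day.

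**Dose at onset: where the taper days fall (200 mg/day steps of 7 days)**

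| Dose before taper | Own band | Taper days in >400–600 | in >200–400 | in ≤200 | Days below own band |
|---|---|---|---|---|---|
| 800 | >600 | 7 | 7 | 7 | 21 of 21 |
| 600 | >400–600 | – | 7 | 7 | 14 of 14 |
| 400 | >200–400 | – | – | 7 | 7 of 7 |

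The result depends on step size. From 400 mg/day in 100 mg/day steps the taper is 300, 200 and 100 for 7 days each. The 7 days at 300 stay in the subject's own band, and 7 + 7 = 14 of 21 days fall in ≤200.

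**Modal dose.** Modal dose = the dose with most days in EP0093; ties go to the lower dose.
- *Constant 800, 600 or 400 mg/day, then taper.* With 7 days of treatment, the pre-taper dose and every taper step tie at 7 days, so the rule picks 200. With fewer than 7 days, the taper steps alone are longest (tied from 600 or 800) and again give 200. With 8 days, the pre-taper dose wins. With 10-day steps the limit moves to 10 days. With 100 mg/day steps from 400, a stay of up to 7 days gives 100.
- *Up-titration: 400 for 7 days, 600 for 7, 800 for x, then taper.* Without taper days, 800 is modal from x = 8. With them, 400 has 7 + 7 = 14 days, 600 has 7 + 7 = 14 and 800 has x. So the modal dose is 400 until x = 14 and 800 from x = 15. For x = 8 to 14, a stay of 14 + x = 22 to 28 days, taper moves the modal dose from 800 to 400.
- *Near-tie in a long stay: 600 for 90 days, 800 for 95 days.* Taper adds 7 days at 600, giving 97 against 95, and the modal dose moves from 800 to 600.

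**The case against.** **The table does what its title says.** Dose at onset reports the dose being taken and makes no claim about maintenance dose. Including taper is an explicit definition, and the safety analysis is descriptive. That stands: the table is not mislabelled. Dose reductions within the Evaluation Period carry a similar ambiguity, which the fix below leaves in place. But the reader still cannot separate the two kinds of exposure in any listed summary table.

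**The by-period summary may still be intended.** SAP 1 defaults to the protocol unless otherwise specified, SAP 3.2.3 uses period dates to classify TEAEs, and SAP 9.2 assigns TEAEs to periods by start date. This stands in part. Yet the table is not in the SAP 9.2 list, the SAP's period definitions combine taper and safety follow-up, and a by-period table alone would not show dose.

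**Stronger readings a reader might draw, which the documents do not support**
- *Low doses will look less well tolerated, or a dose relation will be reversed.* The SAP states no denominator for the dose columns. If it were subjects ever exposed in the band, everyone tapering through ≤200 mg/day would enter it for about a week, which could dilute incidence. The share of subjects kept on low doses is also not given.
- *Withdrawal effects are hidden.* AEs are listed by subject, and CIWA-B is collected at EOS/EDV, end of taper and SFU and is listed. Events starting in the drug-free week or SFU fall after the last dose and enter no dose band. Under Protocol 9.1.1.1, seizures count as AEs only if they change considerably or increase in a clinically significant way.
- *Modal dose distorts the AE results.* No AE table uses it. Nor are stays well beyond a week generally affected: with 7-day steps, 8 days at 400 mg/day against 7 at 200 leaves the modal dose at 400.

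**Conclusion.** The main point holds from the text alone: TEAEs starting in taper enter the dose-at-onset table at the taper dose, and no listed summary table identifies them. Under 7-day steps at the maximum rate, every taper day of a subject at 800, 600 or 400 mg/day lies below that subject's own band; smaller steps reduce the share, to 14 of 21 days in the 400 mg/day variant. The only TEAE-by-dose table is blurred by an amount and in a direction that cannot be stated from the documents.

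The modal-dose point is real but minor. It is confined to stays of about 7 to 10 days at constant dose, short up-titrations (22 to 28 days in the example) and near-ties. It changes only the exposure-by-modal-dose summary; most long stays are unaffected.

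Both points assume that the dose source includes taper doses. The SAP does not name the form that supplies the daily dose for these outputs. However, SAP 3.2.2.1 takes the last dose from the Study Medication Administration eCRF for ongoing subjects who have had the End of Taper Visit, so it treats taper dosing as PSL dosing.

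**What to change.** 1. **SAP 9.2.** Limit the main dose-at-onset bands to TEAEs starting before taper begins. Show taper-onset TEAEs in a separate block with the same four bands, classified by last pre-taper dose. State the denominator for each column.
2. **Cutoff.** Define and use a taper start date, not simply the end of the Evaluation Period. Without an EOS or EDV visit, SAP 3.2.2.4 ends that period at final contact, so any taper dosing in those subjects would still be counted in the main bands. Name the data source for daily dose and taper start.
3. **By-period summary.** Restore the Protocol 12.3 summary by Evaluation, Taper and SFU, or list its removal in SAP 3.9.
4. **SAP 9.1.** Derive modal dose from pre-taper dosing only.
5. **Taper length.** The sponsor must reconcile the four-week description with the footnote giving three weeks plus a drug-free week, since the boundary of the taper block depends on it.

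The cost is SAP wording and one extra table block, plus the by-period table if it is restored. The data are already collected and no event is lost. The downside is fewer events in the main dose bands.
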